#### 7.2.2 Delamanid: Safety in clinical studies

Twelve phase I trials of DLM in healthy adults have shown a favourable side effect profile, with the most commonly reported side effects emerging while on treatment being dizziness, nausea and headache. The total number of adult individuals exposed to DLM in these safety trials has been 949, and overall, the side effects were similar in the groups receiving DLM plus optimized background regimen and the groups receiving placebo plus optimized background regimen.

DLM has been studied in a Phase 2a study in DS-TB patients and placebo-controlled phase 2b and phase 3 trials in MDR-TB. Both in the phase 2b and in the phase 3 studies, the safety profile of DLM in MDR-TB patients was favourable [36]. Serious treatment emergent AEs were similar in patients treated with DLM or placebo on a background regimen in the phase 3 trial that was recently reported. Eight (2.3%) patients in that trial discontinued due to AEs on DLM, compared to three (1.8%) on placebo. The proportion of patients experiencing hepatotoxicity was 6.5% in the DLM arm and 7.1% in the placebo arm, suggesting that DLM did not add to hepatotoxicity of

the background regimen. In the DLM arm, 18 (5.3%) patients experienced a prolongation of their QT interval, as opposed to 5 (2.9%) on placebo.

The QTc prolongation seen in patients treated with DLM is characterized by a slow increase over the first 6-10 weeks of treatment followed by stability, thereafter, appearing to correlate with plasma concentrations of the major metabolite, DM-6705. Both hypoalbuminemia (<2.8 g/dl) and hypokalaemia have been found to be risk factors for DLM associated QTc prolongation.

In the phase 3 study, the mean placebo-corrected QTcF change was 5.3 ms (90% CI: 2.8 - 7.9) at week 8, and 2.5 ms (-0.3 - 5.3) at week 26. Low albumin concentration (DLM is metabolized by albumin) was not associated with higher QTcF prolongation in that study.

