#### Delpazolid

All patients will undergo intensive PK sampling at Day 14 (WK02) visit. A sample will be drawn within 1h before administration of the DZD morning dose (0 h).

The DZD morning dose will be administered with a standardized meal. Blood draws thereafter will be performed at 1, 2, 4, 8, 12 (± 10 mins) and 24 hours (± 30 mins) after DZD morning dose. The exact time of meal and DZD administration at the day of PK sampling will be recorded. Standardized food and fluid intake will be monitored and noted throughout the PK days.

Procedures for sample connection, storage and transportation will be described in the Laboratory Manual. Assaying of DZD, BDQ and DLM plus main metabolites, and MXF will be conducted centrally at the Department of Pharmacy, Radboudumc, the Netherlands, with validated LC-MS/MS methods.

Pharmacokinetic parameters will be assessed using non-compartmental techniques and nonlinear mixed effects methodology. The latter will be utilized to develop a population PK model describing DZD, which will be linked to safety and efficacy parameters. Secondary PK parameters to be reported are listed in section 9.2.3.

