# 12.2 Study drug dosage and administration

The experimental and control treatment as described above will be administered daily for 16 weeks (see Table 1. Daily Dosing of Study Medication), together with food.

- Bedaquiline: will be dosed as per the licensed dose: 400 mg orally once daily for the first 14 days, then 200 mg three times a week.
- Delamanid: will be dosed as per the licensed dose: 200 mg orally in two daily doses of 100 mg.
- Moxifloxacin: will be dosed as per the licensed dose: 400 mg orally once daily
- Delpazolid not licensed:
  - Dose: will be according to randomization to dosing arm:
    - Arm 1: 15 participants will receive 0 mg of DZD
    - Arm 2: 15 participants will receive 400 mg DZD orally once daily
    - Arm 3: 15 participants will receive 800 mg DZD orally once daily
    - Arm 4: 15 participants will receive 1200 mg DZD orally once daily
    - Arm 5: 15 participants will receive 800 mg DZD orally twice daily

The daily dose of study drug for participants will be dependent on the subjects' experimental arm as shown in the following table:

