DZD can be taken with or without food. The bioavailability of BDQ and DLM strongly increases when taken with food. MXF can be taken with or without food. As a result, all anti-TB drugs have to be taken with food and a glass of water in the mornings and evenings.

During pharmacokinetic sampling days, the anti-TB drugs are taken with standardized meals.

As specified under sections 10.4 (page 42) and 12.6.2 (page 60), HIV patients in need of ART will be treated with a dolutegravir-based ART regimen during the study. Dolutegravir in a fixed-dose combination, containing Dolutegravir (50 mg), Lamivudine (300mg) and Tenofovir Disoproxil Fumarate (300mg), will be provided following local clinical practice/procedures and specific recommendations on initiating these drugs. Therefore, this is considered as concomitant medication and not study medication (see also section 12.6).

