5.3. Pharmacokinetics Endpoints

A population PK model will be developed for DZD.

The following secondary parameters will be derived for DZD (model-based), for BDQ and main metabolite M2, DLM and main metabolite DM-6705, and for MXF (with NCA):

• Area under the plasma concentration curve from morning dosing to 24 hours (AUC 0-24) on day 14 (WK02)

- The observed maximum concentration (Cmax) on day 14
- · Time to reach Cmax (Tmax) on day 14
- The minimum observed plasma concentration (Cmin) at day 14 (24 hours following the last dose for QD and 12 hours following the last dose for BID)

Analyses may be limited by available budget, which may lead to parameters for certain drugs not being reported.

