8.4. Model Selection, evaluation and documentation

Model comparisons will be based on the objective function value (OFV), goodness-of-fit plots, precision in parameter estimates and scientific plausibility. A difference in OFV between two nested models is approximately χ^2 -distributed. A difference in OFV \geq 3.84 and 6.63 (one degree of freedom) is thus significant at the 5% and 1% level, respectively.

The final model will be evaluated according to best practice using primarily visual predictive checks (VPCs) and comparison of individual concentration observations and predictions⁷. The model development process will be documented with a run-record exported from Pirana including all key decision points. The popPK dataset, model development process and final model will be described in the popPK model report.

9. Pharmacokinetic analysis companion TB drugs

Non-compartmental PK analysis will be conducted for all the companion drugs (bedaquiline plus metabolite M2, delamanid and moxifloxacin). The following PK parameters will be estimated for day 14 from each participants' individual plasma concentrations by applying a noncompartmental approach using PK software WinNonlin Phoenix or R packages with the same functionality.

Cmax Maximum observed drug concentration

Cmin Minimum observed drug concentration (not including predose observation)

Tmax Time of the maximum drug concentration (obtained without interpolation)

AUC(0-24H) Area under the drug concentration-time curve calculated using Log linear trapezoidal summation from time zero

to time 24 h post dose

In addition, for moxifloxacin the following parameters will be reported:

Kel Terminal elimination rate constant calculated by linear regression of the terminal linear portion of the log concentration vs. time curve

T½ Elimination half-life calculated as ln(2)/Kel

CL/F Apparent oral clearance [Dose/AUC(0-24H)]

Vd/F Apparent volume of distribution following oral administration [Vd/F = (CL/F)/Kel]

The actual elapsed time will be calculated from actual dosing and sampling times and used in the parameter estimation.

The rate constant of the elimination phase (λ_z) will be calculated by log-linear regression of the terminal portion of the concentration-time profile where there are sufficient data (i.e. at least 3 time points and the correlation coefficients for the terminal slope $[R^2]$ is greater than or equal to 0.9). If these criteria are not fulfilled, λ_z and $t_{1/2}$ will not be reported.

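### The 0-24 h trapezoid in SAP 9 misses delamanid's evening peak when the evening dose follows the 12 h sample, and the SAP 9 analyte list omits DM-6705, which SAP 5.3 includes

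*SAP*

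**What the plan says.** SAP 9 plans a non-compartmental analysis on day 14 for every companion drug, with a single definition of daily exposure: "AUC(0-24H) Area under the drug concentration-time curve calculated using Log linear trapezoidal summation", running from time zero to 24 h. It has no provision for a second dose inside that interval.

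Delamanid is the only companion drug dosed twice a day. Protocol 12.2 gives it as "200 mg orally in two daily doses of 100 mg", and the text after Table 1 says the anti-TB drugs "have to be taken with food and a glass of water in the mornings and evenings". No clock time is set for the evening intake.

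Protocol 11.5 takes a pre-dose sample and then states: "Blood draws thereafter will be performed at 1, 2, 4, 8, 12 (± 10 mins) and 24 hours (± 30 mins) after DZD morning dose". That makes seven samples, with none between 12 and 24 h.

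On analytes, SAP 5.3 lists "DLM and main metabolite DM-6705" among the non-compartmental endpoints, while SAP 9 names "bedaquiline plus metabolite M2, delamanid and moxifloxacin". Protocol 7.2.2 describes the QTc effect of delamanid as "appearing to correlate with plasma concentrations of the major metabolite, DM-6705".

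**The concern.** A trapezoid is sound when the samples follow the shape of the curve. For once-daily bedaquiline and moxifloxacin they do. For delamanid the curve rises again after the evening dose. If that dose comes just after the 12 h draw, the 12 h and 24 h samples are both near-trough values, and the line between them cuts off the evening peak. This error is structural, so more patients do not reduce it.

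Describing companion-drug PK is the secondary PK objective. Readers will naturally set the delamanid result beside the 7234 h*ng/mL that Protocol 7.2.3 quotes for the same regimen at two weeks. The SAP also contradicts itself on whether DM-6705, the metabolite the protocol ties to QTc, is analysed.

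**Working it through.** The documents give no bias figure for this analysis, so there is none to reproduce.

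**Inputs from Protocol 7.2.3.** Delamanid Tmax 4 h; terminal half-life 30-38 h; main metabolites' half-life 150-600 h; CV of AUC 32% at two weeks; once-daily 200 mg in healthy subjects: AUC 5,950 ng·h/mL, Cmax 476 (SD 119) ng/mL.

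**Assumed.** One compartment, first-order absorption, equal morning and evening doses, and an evening dose time varied from 9 to 14 h.

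**Model.** ke = ln2/t½, and ka solves ln(ka/ke)/(ka − ke) = 4. Each dose at time d adds ka/(ka − ke) × [exp(−ke(t − d)) − exp(−ka(t − d))]. Doses are summed over 13 earlier days plus the PK day. Bias = 100 × (estimate / true AUC0-24 − 1), where the estimate uses samples at 0, 1, 2, 4, 8, 12 and 24 h (linear when rising, logarithmic when falling).

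**Half-life.** The once-daily figures imply Cmax/Cavg = 476/(5,950/24) = 1.92. A 34 h half-life in this model gives only 1.19; matching 1.92 needs about 5.8 h. The terminal half-life may therefore understate how sharply concentrations peak within a dosing interval, so both cases are shown.

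| Evening dose | t½ 30-38 h: planned rule | t½ 30-38 h: 2 x AUC0-12 | t½ 5.8 h: planned rule | t½ 5.8 h: 2 x AUC0-12 |
|---|---|---|---|---|
| 9 h | −0.5 to −0.6% | +0.7 to +0.9% | −4.7% | +5.2% |
| 10 h | −0.1 to −0.3% | +1.2 to +1.5% | −4.8% | +5.7% |
| 11 h | −0.9 to −1.2% | +1.3 to +1.5% | −8.7% | +4.0% |
| 12 h, just after the sample | −4.6 to −5.7% | −0.3% | −20.7% | −1.6% |
| 13 h | −3.8 to −4.6% | +0.6 to +0.7% | −17.2% | +1.6% |
| 14 h | −2.9 to −3.6% | +1.4 to +1.8% | −13.5% | +5.2% |

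With the dose at 12 h, the 12-24 h segment alone is 9-11% low (long half-life) or about 40% low (short). With Cmax one SD lower, the ratio is (476 − 119)/(5,950/24) = 1.44, the fitted half-life is 14 h and the bias is −11%. At 12 h or later, the choice of trapezoid (linear, mixed or fully logarithmic) matters by less than 1 point.

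**In the protocol's units.** If the true mean were 7234 h*ng/mL, a 12 h evening dose would give 7234 × (1 − 0.046) = 6,901 to 7234 × (1 − 0.057) = 6,822, or 7234 × (1 − 0.207) = 5,737 in the short half-life case.

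**Sampling error.** 32%/√15 = 8.3% for one dose group; 32%/√75 = 3.7% for all arms pooled.

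**DM-6705.** With a half-life of 150-600 h the curve is almost flat over a day, and the planned trapezoid is biased by less than 0.2%. Concentrations are still rising: after 14 days (336 h) they are at 1 − 2^(−336/150) = 79% to 1 − 2^(−336/600) = 32% of steady state. Doubling AUC0-12 would therefore read about 1-2% low.

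**The case against.** The strongest counter-argument is that the consequences are small, and much of it stands.

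- **A reader might infer a false delpazolid interaction.** The documents do not support that between arms. All five arms, including the one without delpazolid, share the delamanid dose and sampling times, and SAP 9 summarises PK by dose group, so a common bias largely cancels. A misleading signal would need a comparison with an outside figure, which neither document plans formally.
- **A reader might infer that the bias exceeds the sampling error.** That holds against the pooled 3.7%. Reporting is by dose group, where the standard error is 8.3%, above the 4.6-5.7% of the long half-life case.
- **A reader might infer that every patient's AUC is materially too low.** This depends on the evening dose time. SAP 5.3 and Protocol 9.2.3 place the twice-daily Cmin at 12 h after the dose, which suggests that the 12 h sample is meant as a pre-dose trough, but nothing fixes the order. With a 9-11 h dose and a long half-life the bias nearly vanishes.
- **A reader might infer that DM-6705 has been dropped from the trial.** It has not. SAP 5.3 names the analyte, method and parameters, and Protocol 11.5 plans the assay. Only the SAP 9 list is incomplete. The SAP's ECG section plans no concentration-QTcF analysis, so no specified analysis is lost.

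Both documents also allow some PK parameters to go unreported for budget reasons. SAP 9 permits documented case-by-case deviations, but that allowance follows its rules for values below the quantification limit and is no method for a second dose. None of this shows that the stated rule suits a twice-daily drug without afternoon-to-morning sampling.

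**Conclusion.** The point holds for the absolute delamanid AUC0-24. When the evening dose follows the 12 h sample, the rule in SAP 9 is biased low: by about 5-6% for a dose at 12 h with the protocol's Tmax and half-life, and up to about 20% if the effective half-life is about 6 h. With the evening dose at 9-11 h it is about 0-1% (long half-life) or 5-9% (short). These sizes rest on a one-compartment model and an unstated dose time; the short half-life is fitted to healthy-subject data.

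The harm is to a secondary, descriptive parameter and to its comparison with outside values. Comparisons between arms are hardly affected, and the delpazolid exposure-response analysis uses delpazolid metrics from its own population model. SAP 9 derives clearance only for moxifloxacin, so the error does not pass into a delamanid clearance. The DM-6705 gap is an inconsistency between SAP 5.3 and SAP 9. The correction is worth making because it needs only wording.

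**What to change.** In SAP 9:

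1. For delamanid, compute AUC0-12 from the 0-12 h samples and report AUC0-24 as 2 x AUC0-12 when recorded times show that the 12 h sample preceded the evening dose.
2. State a rule for exceptions, covering an evening dose before the 12 h sample and a missing evening dose time. One option is to keep the 0-24 h trapezoid for these patients and flag the values, because doubling then overstates AUC0-24 by about 1-6% in the scenarios above.
3. Keep the 0-24 h trapezoid for bedaquiline and M2, moxifloxacin and DM-6705.
4. Add DM-6705 to the analyte list to match SAP 5.3, and label its results as day 14, not steady state.

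The cost is SAP wording: the samples and assays are already planned, and the schedule of events already has drug intake times recorded on the PK day. The downside is that 2 x AUC0-12 assumes equal morning and evening exposure, which this sampling schedule cannot check. If the evening dose is well after 12 h, doubling overstates AUC0-24 somewhat (up to 1.8% with the long half-life and 5.2% with the short, at 14 h), still less than the planned rule understates it.

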10.1. Base model of TTP

Time to positivity (TTP) in the MGIT system will be analysed to evaluate efficacy. The model for TTP will be based on previously developed and published models.

Option 1: Semi-mechanistic model linking a latent variable describing the decline in bacterial load to a model of probability of detection in MGIT (handling negative samples) and a time-to-event model for TTP.⁸ The TTP value measured at baseline will be used to individualize the starting point for each patient. Only TTP values measured after start of treatment will be included in the fit of the model. Inter-individual variability with long-normal distributions will be included for parameters describing the bacterial load at baseline and the decline in bacterial load.

Option 2: Bi-linear models with estimated inflexion-point and negative cultures handled by the M3 method (estimating a probability of negative sample at the given time)^{9,10}

Option 3: Shifted logistic model and negative cultures handled by the M3 method⁹¹¹.

The models may be adjusted as needed to achieve a satisfactory fit of the observed data. The fit will be evaluated primarily with two types of goodness of fit plots: visual predictive checks of the proportion of negative samples over time on treatment and Kaplan-Meier visual predictive checks of TTP per treatment week (for option 1) and visual predictive checks of quantitative TTP over time on treatment (for option 2 and 3). The choice of model to use for the exposure-response evaluation will be based on the mentioned goodness-of-fit plots, the objective function value, precision in estimated model parameters and estimation stability (successful convergence of estimation algorithm).

10.2. Exposure-response model

The following PK parameters (derived from the popPK model) will be considered in the exposure response analysis: delpazolidAUC0-24h, Cmax and Cmin from day 14 morning dose. The PK parameters will be evaluated as predictors for the decline in bacterial load and the following relations will be tested: linear, Emax and sigmoid Emax. Likelihood ratio tests and a 5%-significance level will be used for testing the statistical significance of inclusion of PK effects.

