## 5 RATIONALE FOR THE STUDY

New TB treatment regimens are vital to combat the TB epidemic, and most importantly, the drugresistant TB epidemic.

In MDR-TB, only 52% of MDR cases achieve cure [1]. A model of MDR-TB in Vietnam showed that under current diagnostic and treatment practices, MDR-TB incidence will increase by 17%, and deaths by 22%, within ten years [10]. In a similar model in China, MDR-TB will become the dominant form of TB by 2050 [2].

To effectively combat this epidemic, more potent drug combinations with regards to sterilizing capacity are necessary. These can be created through introduction of novel drugs with a low pre-existing resistance.

As evidenced by the success of the Nix-TB regimen composed of BDQ, a nitroimidazole, and LZD in patients with high levels of drug resistance, this drug combination is effective in curing TB within 6 months of treatment.

DZD in combination with BDM, is key in advancing a TB regimen with low pre-existing resistance and improved tolerability compared to LZD containing regimens.

DZD has a good safety profile, as has been assessed both pre-clinically and clinically for up to 21 days in healthy volunteers.

Previously DZD has been studied in patients in an EBA monotherapy study. DZD showed good activity in this study [11], but the question of selecting the best possible dose is not answered yet, since a reliable dose-response was not observed then.

A 14-day EBA is not long enough to assess the safety of different doses of DZD, since oxazolidinone class toxicity usually becomes apparent at a later stage in treatment.

Based on this, we believe it is more valuable to evaluate DZD over a dosing period which will generate enough accurate data on efficacy and safety to link exposure to safety observations. A time-period of dosing for 4 months is minimal to get a reliable estimate of toxicity, given that oxazolidinone class toxicity occurs not immediately during therapy [7].

A U.S. FDA guidance recently described an incompletely understood dose-toxicity and dose-response relationship as the cause for failure of many drug development programmes. It suggested testing several doses in phase IIb, and then continuing one or two selected doses [12].

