# 13.5 Procedures to assign participants to treatment groups

Patients who have given informed consent and who have been found eligible for participation (meeting all inclusion criteria and no exclusion criterion) based on results from screening visit, will be randomly assigned to one out of five treatment arms with a 1:1:1:1:1 allocation. Randomization must be performed when all screening results are available but not before eligibility for study participation is proven.

Randomization will be performed through centralized assignment of patients by means of an Interactive Web Response System (IWRS), a web-based randomization system. Patient characteristics will be used to balance the composition of the treatment arms with regards to prognostic factors.

These characteristics will be:

- site
- HIV status
- bacterial load in sputum as measured by GeneXpert cycle threshold

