3.1. Safety and Tolerability Objective

To describe the safety, tolerability and exposure-toxicity relationship of delpazolid (DZD) given over 16 weeks, in combination with standard-dose BDQ, DLM and MXF, compared to standard dose BDQ, DLM and MXF alone.

The aim is to identify the optimal dose of DZD to be used in subsequent studies that provides the best efficacy at acceptable safety of the drug when given daily over 4 months in patients with newly diagnosed, uncomplicated, smear-positive, drug-sensitive, pulmonary tuberculosis.

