4.3. Sample Size Determination

15 participants per arm with a total of 75 participants, and a wide range of DZD doses (from 0mg to 800mg BID) has been determined as an adequate sample size for population PK modelling, and for exposure response modelling to detect a clinically meaningful dose-dependent relationship.

Furthermore, the planned sample size of 15 participants per treatment group is in keeping with other trials of this type and accounts for the possibility of up to 3 drop-outs per group, which based on previous studies of this type conducted at these sites, represents a conservative estimate of the expected drop-out rate.

Previous Phase IIA (EBA) studies indicate that the between patient standard deviation of logCFU can be approximately 0.2. Therefore, assuming similar variability in this trial the expected standard errors of group mean EBA and corresponding width of 95% confidence intervals are 0.052 and 0.101 respectively for a group size of 15 and 0.063 and 0.124 respectively for a group size of 10.

This level of precision with a group size of 15 is considered adequate.

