10.3. Other covariates

Patient characteristics may influence the TTP dynamics, like the severity of disease at start of treatment (degree of cavitation, baseline bacterial load), co-infection with HIV, sex, adherence to treatment, etc. Those factors will be evaluated as predictors for the decline in bacterial load. Likelihood ratio tests and a 5%-significance level will be used for testing the statistical significance of inclusion of covariate effects.

Parameter estimates with corresponding uncertainty for the final model will be reported.

11. Outcome Definitions

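### If no exposure term passes its 5% likelihood ratio test, the primary TTP analysis has no planned estimate or confidence limit for the DZD effect

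*SAP*

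**What the plan says.** SAP section 10 is the primary efficacy analysis. Section 10.2 takes three day-14 exposure metrics from the population PK model (AUC0-24h, plus "Cmax and Cmin from day 14 morning dose") as predictors of the decline in bacterial load, and "the following relations will be tested: linear, Emax and sigmoid Emax". That makes nine metric-by-shape candidates. The entry criterion is: "Likelihood ratio tests and a 5%-significance level will be used for testing the statistical significance of inclusion of PK effects".

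Section 10.3 then states: "Parameter estimates with corresponding uncertainty for the final model will be reported". Neither section plans an estimate or interval for an exposure term that is not retained, and neither says how a non-significant test will be read.

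On purpose, SAP 3.1 states: "The aim is to identify the optimal dose of DZD to be used in subsequent studies". SAP 3.2.2 adds a secondary objective of judging increasing doses against the background regimen on the primary as well as the secondary endpoints.

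The size is "15 participants per arm with a total of 75 participants" (SAP 4.3), and Protocol 13.5 has patients "randomly assigned to one out of five treatment arms with a 1:1:1:1:1 allocation". No power or target effect is given for the exposure test.

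**The concern.** Using a significance test to decide whether a covariate enters is ordinary practice for nuisance covariates. Here the tested term is the trial's primary question. If it fails the test and only the final model is reported, the primary analysis contains no DZD parameter, so nothing shows how large a benefit the data still allow. If it passes, the reported slope has been selected for being large and tends to be overstated when carried into dose simulations.

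A non-significant result is conceivable. Of the earlier early bactericidal activity (EBA) study, Protocol section 5 says that "a reliable dose-response was not observed then". At stake is whether the trial can inform dose choice on TTP when p exceeds 0.05.

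**Working it through.** **1. The plan's own precision figures.** SAP 4.3 and Protocol 15.1 use a between-patient SD of 0.2 on the EBA logCFU scale.
- n = 15: SE = 0.2/√15 = 0.052; 1.96 × SE = 0.101.
- n = 10: SE = 0.2/√10 = 0.063; 1.96 × SE = 0.124.

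All four figures reproduce, provided that the stated CI width means the half-width (the full widths are 0.202 and 0.248). They describe one group mean on an EBA scale and say nothing about the exposure test on TTP.

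**2. Assumptions, because the documents give no figure.** The effect is a 0.5-SD difference in decline rate between no DZD and typical 1600 mg/day exposure, in between-patient SDs (0.1 on the EBA scale if SD is 0.2). AUC CV is 20-50%. Each patient contributes one decline rate. Group sizes are 15 per arm, and 12 per arm after the 3 drop-outs per group that SAP 4.3 allows for.

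**3. Hand check with a linear dose trend.** Doses of 0, 400, 800, 1200 and 1600 mg/day have SD √320,000 = 565.7.
- 75 patients: noncentrality = √75 × 0.5 × 565.7/1600 = 1.531; power = Φ(1.531 − 1.96) = 33%, so 67% missed.
- 60 patients: noncentrality 1.369; power 28%, so 72% missed.
- 95% half-width for the 0-to-1600 effect: 1.96 × 1600/(565.7 × √75) = 0.64 SD; with 60 patients, 0.72 SD.
- Effect detectable with 80% power, 75 patients: (1.96 + 0.84) × 1600/(565.7 × √75) ≈ 0.92 SD.

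An estimate of zero would therefore still be compatible with a 0.5-SD benefit.

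**4. Simulated likelihood ratio test on individual AUC.** Relative exposures are 0, 0.25, 0.5, 0.75 and 1 with log-normal variability. The true effect is linear and the critical value is 3.84. Typical exposure is taken as the arm mean AUC:

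| AUC CV | 0.5 SD missed, 15/arm | 0.5 SD missed, 12/arm | 0.8 SD missed, 15/arm |
|---|---|---|---|
| 20% | 63% | 68% | 27% |
| 35% | 57% | 63% | 20% |
| 50% | 48% | 56% | 13% |

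If typical exposure is instead the median, which fits the log-normal model in SAP 8.3.2, the 0.5-SD misses are about 40-62% at 15 per arm and 49-68% at 12 per arm. The lowest 0.8-SD figure falls to about 7%.

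**5. Any of the nine candidates may enter (0.5 SD, 15 per arm).**
- Linear truth: 46% missed at AUC CV 30%, 30% at CV 50%.
- At CV 30%, an Emax truth gives 58% and a step truth 61%.
- With no true effect, some exposure term enters in about 13% of trials.

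**6. What the two outcomes would show (0.5 SD, linear AUC, 15 per arm).** Among non-significant trials, about 95% have an upper 95% limit of at least 0.5 SD, with a median limit of 0.83-0.96 SD (arm-mean scaling). Among significant trials, the slope is overstated by roughly 30-60%.

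**7. What else is planned on DZD.** Table 2.7 gives TTP by arm and week as mean (SD), median and range, with no contrast. SAP 12.1 and Tables 2.8-2.9 give hazard ratios with 95% CIs by dose arm for time to culture conversion, and SAP 12.1 gives Kaplan-Meier proportions with CIs. These are dose-based analyses of a secondary endpoint.

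**The case against.** The strongest reply is that the SAP does not forbid reporting a tested but unretained exposure model. A reader might infer that p > 0.05 will be declared to mean no exposure-response, or that the doses will be treated as equivalent. No such rule appears in either document, and dose choice is tied to the trial's data on efficacy and safety, not to this p-value. That stands: it is a foreseeable misreading, not plan text.

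A reader might also infer that the trial would have no bound at all on the DZD effect. That goes too far, because the culture-conversion analyses give intervals by arm whatever this test shows. They do not bound the exposure effect on TTP, so the gap is confined to the primary model.

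Third, the miss rates depend on assumptions. They fall to about 30% when all nine candidates may enter, the truth is linear and AUC CV is 50%, and a 0.8-SD effect is missed far less often. If 0.5 SD meant per SD of exposure, only 1-3% of trials would miss it. A flat statement that the test misses real effects at least half the time is therefore unsupported. In the other direction, censored negative cultures and the exclusion of TTP after discontinuation would lower power.

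Finally, the EBA study compared active doses of 800-1600 mg/day only. This trial adds 0 and 400 mg/day, so the EBA result does not by itself predict a null test here.

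**Conclusion.** The point holds as a reporting gap in the primary analysis. SAP 10.2 and 10.3 together leave no planned estimate or confidence limit for the DZD effect on TTP when no exposure term is retained, and no other planned output supplies one for that endpoint.

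Under the stated assumptions for 0.5 SD, a single linear-AUC test misses the effect in roughly 40-63% of trials at 15 per arm and 49-68% at 12 per arm. With all nine candidates and a linear truth, the figure is about 30-46% at 15 per arm. A 0.8-SD effect is missed in roughly 7-27% at 15 per arm by the single test. Even the lower figures for 0.5 SD are too high to take a non-significant test as evidence of no effect. The exact rates should not be quoted without the assumed effect, contrast and AUC variability.

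**What to change.** Keep the likelihood ratio tests for building the model. Add to SAP 10.2-10.3 that:
- a prespecified exposure-effect model is always fitted and reported with its estimate and 95% CI whatever the p-value. Linear AUC0-24 on decline in bacterial load is one example; any better-fitting retained form would be shown alongside it;
- the effect is expressed as the change in decline rate at typical exposure in each arm versus zero exposure;
- a non-significant test is not read as equal efficacy of the doses, and the dose discussion uses the interval.

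The choice of linear AUC is not essential; what matters is that one form is named in advance. The cost is one or two sentences and one table, from a model that is run in any case. No new data or patients are needed.
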